11.2 Sample Size Calculations

The sample size calculation for the primary efficacy analysis of the comparison of median overall survival between the two groups is based on the assumption of a 16 month median survival in the cTACE group and a 24 month median survival in the hqTACE group. A sample size of 196 patients per treatment group will have 85% power to detect this difference in median survival (Hazard ratio= 1.500) based on a 2-sided Type I error rate of 5%. Assuming a 30% non-evaluable rate, a total of 255 patients will be enrolled and randomized into each treatment group.

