11.3.2 Intent-to-Treat Population (ITT)

The Intent- to-Treat (ITT) Population is defined as all patients randomized in the study, regardless of treatment status. This will be the primary population for the efficacy analyses.

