11.5 Efficacy Analysis

11.5.1 Median Overall Survival

The primary efficacy analysis of median overall survival will be performed on the ITT population when the last patient has completed two years of follow-up after their first study TACE procedure or 218 deaths have been observed in the two groups combined, whichever comes first. Patients will be followed for survival until death or loss to follow up. Overall survival time will be calculated in months from the date of the first study TACE embolization to the date of death or date last known to be alive for patients who are lost to follow up. Median overall survival time will be calculated for each treatment group using the Kaplan-Meier (product-limit) method and corresponding 95% confidence intervals will be generated. Treatment groups will be compared on median survival using a log-rank test.

One and two year survival rates and corresponding 95% confidence intervals will also be calculated for both treatment groups. Survival analyses will also be performed for the Evaluable population.

In order to assess the consistency of observed treatment effect across investigational sites, a data poolability analysis will be performed on the primary efficacy outcome of overall survival using the ITT population. Median overall survival data will be summarized by site, including Kaplan-Meier plots. In addition, a Cox proportional hazards model will be run including factors for treatment group, investigational site, and an interaction term for treatment group and investigational site. For purposes of this analysis, sites enrolling fewer than 10 patients may be pooled into a single site.

A multivariate analysis of the primary efficacy outcome of overall survival will be performed using a Cox proportional hazards model for the ITT population. This analysis will be considered supportive only. The model will include factors for site, as well as all variables included in the final adaptive randomization model. In addition, key baseline factors found to be significantly different between the two treatment groups at baseline will also be evaluated in the model.

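### Section 11.2: 255 patients per group allows for about 23% non-evaluable patients, not the stated 30%

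*Combined protocol and SAP*

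**What the plan says.** Section 11.2 (Sample Size Calculations) is "based on the assumption of a 16 month median survival in the cTACE group" and "a 24 month median survival in the hqTACE group", given there as "Hazard ratio= 1.500", with a two-sided 5% error rate. On this basis, "A sample size of 196 patients per treatment group will have 85% power to detect this difference in median survival". The section then allows for losses: "Assuming a 30% non-evaluable rate, a total of 255 patients will be enrolled and randomized into each treatment group". It shows no formula for going from 196 to 255, does not say what the 30% is a percentage of, and does not define non-evaluable.

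Three other places bear on what the figure means:

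- Section 11.3.2 defines the ITT population as everyone randomized and says of it: "This will be the primary population for the efficacy analyses".
- Section 11.5.1 runs the primary survival analysis on that population, either two years after the last patient's first TACE or when "218 deaths have been observed in the two groups combined, whichever comes first".
- The Withdrawal of Patients section rules out replacing patients who withdraw, so later recruitment does not make up any shortfall.

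**The concern.** A non-evaluable rate ordinarily means the share of enrolled patients who turn out not to be usable. To keep a required number n after losing a share d of those enrolled, one enrols n/(1 - d). The plan's 255 is what results from n x (1 + d), which is always too small. At d = 0.30 the gap is large enough to notice.

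Section 11.2 is the only place where the plan says how much loss its enrolment can absorb. Anyone comparing observed losses with 30% would think the trial still within its design when the number it set out to keep had already been missed. The Evaluable-population analyses of survival (11.5.1) and objective response (11.5.2) would feel the shortfall directly, although the plan sets no power target for them. For the primary analysis, the question is whether the slip affects power at all.

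**Working it through.** **Inputs.** From 11.2: medians of 16 and 24 months, hazard ratio 1.5, 85% power, two-sided alpha 5%, 196 per group before inflation, 30% loss, 255 per group after inflation. From Study Design: 1:1 allocation. From 11.5.1: 218 deaths, or two years after the last patient's first TACE.

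**1. Reproduce the base figure of 196.** Section 11.2 gives no accrual or follow-up time, so I assume exponential survival and 24 months of follow-up for everyone.

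- Deaths by 24 months: cTACE 1 - 2^(-24/16) = 64.6%; hqTACE 1 - 2^(-24/24) = 50.0%; mean 57.3%.
- Deaths needed for 85% power: Freedman 224.5, rounded up to 225; Schoenfeld 218.4, rounded up to 219.
- Patients: 225/0.573 = 392.5 in total, about 196 per group (Freedman); 219/0.573 gives about 191 per group (Schoenfeld).

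The base figure reproduces. The problem lies in the inflation step alone, and that step does not depend on the follow-up assumption.

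**2. Reproduce 255.**

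| Formula | Result per group |
|---|---|
| n x (1 + d) = 196 x 1.30 | 254.8, rounded to 255 |
| n/(1 - d) = 196/0.70 | 280 |

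Only the first gives the plan's number. The plan does not show this step; it is inferred from the match.

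**3. What 255 delivers.** This does not depend on how 255 was reached.

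- Left after a 30% loss: 255 x 0.70 = 178.5 per group (357 in total), and 178.5/196 = 0.911, about 9% short.
- Loss at which 196 remain: (255 - 196)/255 = 59/255 = 23.1%. Check: 255 x 0.77 = 196.35.
- Enrolment that matches a 30% loss: 280 per group (560 in total) against 255 (510 in total), a gap of 25 per group and 50 overall.

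**4. Effect on the primary analysis.** Power of the log-rank test depends on the number of deaths. At 218 deaths with 1:1 allocation:

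- Schoenfeld: Phi(sqrt(218) x ln(1.5)/2 - 1.960) = 84.9%.
- Freedman: Phi(sqrt(218) x (1.5 - 1)/(1.5 + 1) - 1.960) = 84.0%.

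The trigger is 218/510 = 42.7% of those randomized. With 24 months of follow-up for everyone, 510 patients would give about 510 x 0.573 = 292 deaths, well above 218.

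**5. A pessimistic bound.** Suppose the non-evaluable 30% contributed nothing at all to the survival analysis. The remaining 357 patients would give about 357 x 0.573 = 205 deaths at 24 months, and power would be about 82-83% (Schoenfeld). This is an illustration: it gives lost patients no follow-up time and gives early enrollees none beyond 24 months.

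**The case against.** The strongest objection is that almost nothing follows from the slip. Patients classed as non-evaluable stay in the ITT analysis, that analysis is tied to deaths, and even the pessimistic bound costs only two or three points of power. This stands, and it is why the point is minor.

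A second objection is that 11.2 names no denominator. If the 30% is read as an over-enrolment margin on the 196 required, then 59/196 = 30.1% and the figures agree. That reading is possible, but it is not what a non-evaluable rate ordinarily means, and the sentence concerns patients enrolled and randomized. If a margin was intended, the sentence still needs rewording, because most readers will take 30% as a share of those enrolled. What does stand is that the calculation here is conditional on that denominator. It does not depend on which patients count as non-evaluable.

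A third objection is that lowering the stated tolerance to 23% fits the assumption to the number if the sponsor really expects a 30% loss. That is fair. The statement should therefore also show what remains at 30%, so that the expected loss is not hidden.

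**Conclusion.** The sentence is wrong as written. With the rate taken as a share of enrolled patients, 255 per group tolerates 23.1%, not 30%. At 30% it leaves about 178 per group instead of 196. The error is confined to the stated loss allowance. The base figure of 196 reproduces, and 218 deaths give 84-85% power for the assumed hazard ratio, so the primary test is essentially unaffected.

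There is one limit on that reassurance. Section 11.5.1 starts the survival clock at treatment: "Overall survival time will be calculated in months from the date of the first study TACE embolization to the date of death". A randomized patient who never receives TACE has no start date, so the ITT definition alone does not guarantee that every randomized patient contributes to the analysis. The effect of such cases cannot be sized from the documents; the 82-83% above indicates the scale if losses of that kind reached 30%.

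Severity: minor.

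**What to change.** Replace the last sentence of 11.2 with wording such as: *Enrolling 255 patients per group leaves 196 if up to 23% of those enrolled are non-evaluable, and about 178 if 30% are. The primary ITT analysis at 218 deaths has about 85% power for a hazard ratio of 1.5.*

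The same edit should say what non-evaluable means here, since 11.3.3 defines an Evaluable population and 11.2 does not say whether it refers to that.

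The cost is a change to one sentence and a lower stated tolerance. The enrolment, test, analysis population, event trigger and primary power do not change. If the sponsor instead wants to keep 196 per group after a true 30% loss, the consistent enrolment figure is 280 per group, 50 more patients in total; the primary analysis does not require this.

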11.3 Analysis Populations

11.3.1 Safety Population (SAF)

All randomized patients who have at least one TACE procedure will be included in the Safety Population.

11.3.2 Intent-to-Treat Population (ITT)

The Intent- to-Treat (ITT) Population is defined as all patients randomized in the study, regardless of treatment status. This will be the primary population for the efficacy analyses.

11.3.3 Evaluable Population (EVAL)

All randomized patients who have at least one TACE procedure and who have at least one post-baseline tumor evaluation and who do not have any major protocol violations will be included in the Evaluable Population.

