7.2 First TACE Cycle

A TACE cycle is defined as a single embolization for patients with unilobar disease or an embolization of each lobe for patients with bilobar disease.

First TACE embolization must be within 4 weeks (\pm 1 week) of baseline MRI and laboratory evaluations.

If a patient has bilobar disease, the first lobe must undergo chemoembolization within 4 weeks (\pm 1 week) of baseline MRI and laboratory evaluations, and the second lobe must undergo chemoembolization within 4 weeks (\pm 1 week) of the first lobe.

A blood sample will be drawn the morning after the first embolization between 6am and 8am for PK analysis for all patients. For patients with bilobar disease, this sample is drawn after the embolization of the first lobe. An additional PK blood sample will be drawn 6-8 hours after the first sample for those patients who have not been discharged.

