APPENDIX A

1. Study Flowchart: Unilobar Disease

[figure not shown]
2. Study Flowchart: Bilobar Disease

3. Schedule of Study Events

1. Study Flowchart: Patients with Unilobar Disease

2. Study Flowchart: Patients with Bilobar Disease

3. Schedule of Procedures						
	Screening (within 4 weeks +/- 1 week of first TACE)	TACE Treatment Period ¹			Post-final TACE Study Visit ²	Survival Follow- up ³
	Visit -1	Tx Visit 1	Tx Visit 2	Tx Visit 3	Visit 4	
Informed Consent	X					
Eligibility criteria assessment	X					
Demographics	X					
Baseline HCC Review ⁴	X					
Medical History	X					
Concurrent Medical Conditions	X					
Physical Examination ⁵	X				X	
Vital signs	X				X	
Serum Pregnancy test	X					
Hematology / Serum Chemistry ⁶	X	X	X	X	X	
Urinalysis	X	X	X	X	X	
Tumor Evaluations (MRI) ⁶	X	X	X	X		
Alpha-feto protein (AFP) ⁶	X	X	X	X	X	
12-lead ECG	X				X	
Cardiac Ejection Fraction ⁷	X		X		X	
Randomization ⁸						
Embolization procedures (TACE)		X	X	X		
Resource Utilization		X	X	X		
Adverse Events		From randomization to protocol defined follow- up period				
Concomitant Medications		X				
Protocol deviations/violations		X				
Survival status						X
Additional cancer treatments						X
Pharmacokinetic Sampling ⁹		X				

¹ First TACE Cycle must be begin within 4 weeks (± 1 week) of baseline MRI and labs. If the patient has bilobar disease, the embolization of the first lobe must be within 4 weeks (± 1 week) of baseline MRI and labs and the second lobe must undergo embolization within 4 weeks (± 1 week) of the first lobe.

A second TACE cycle is required for all patients, unless the investigator deems further treatment unsafe for the patient. The second TACE cycle must be within 8 weeks (± 2 weeks) of first TACE cycle. If the patient has bilobar disease, the first lobe of the second TACE cycle must undergo chemoembolization within 8 weeks (± 2 weeks) of the second lobe in the first TACE cycle, and the second lobe of the second TACE cycle must undergo chemoembolization within 4 weeks (± 1 week) of first lobe in the second TACE cycle.

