A third TACE cycle will be done for patients with MRI results for the liver after the second TACE cycle that demonstrate less than complete necrosis, as interpreted by the Central Reviewers, according to mRECIST criteria. The third TACE cycle must be done within 8 weeks (± 2 weeks) of the second TACE cycle. If the patient has bilobar disease, the first lobe of the third TACE cycle must undergo chemoembolization within 8 weeks (± 2 weeks) of the second lobe of the second TACE cycle, and the second lobe of the third TACE cycle must undergo chemoembolization within 4 weeks (± 1 week) of the first lobe in the third TACE cycle.

² Post final TACE study visit must occur within 4 weeks (± 1 week) of the final study MRI.

³ Patients will be followed for survival for 2 years after the first TACE embolization. Survival contacts will be performed every 3 months.

⁴ Includes baseline disease status (Child Pugh, Unilobar/Bilobar status, ECOG), prior hepatic treatments, risk factor assessment, and assessment for relevant baseline medical conditions.

⁵ Physical exam for the Post final TACE visit must be within 4 weeks (± 1 week) of final study MRI.

⁶ MRIs and labs (including AFP) will be performed 4 weeks (± 1 week) after each TACE cycle. For patients with bilobar disease, MRI must be within 4 weeks (± 1 week) of the second lobe embolization.

⁷ Cardiac ejection fraction may also be assessed as clinically indicated to evaluate a cardiac adverse event.

⁸ Randomization will occur as close to the day of the scheduled First TACE procedure as possible, preferably on the same day.

⁹ A blood sample will be drawn for PK analysis between 6a and 8a the day after the first embolization of the first TACE Cycle, again 6-8 hours later for patients who have not been discharged at that time, and on the day of the first follow-up MRI.

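### Evaluable-population survival is timed from the first TACE but admits only patients with a later MRI, so deaths before that MRI are excluded and the reported medians and survival rates are too high

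*Combined protocol and SAP*

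**What the plan says.** Protocol section 11.3.3 requires at least one TACE procedure and then restricts the population to patients "who have at least one post-baseline tumor evaluation" and no major protocol violation. In this trial a tumor evaluation is an MRI (Schedule of Procedures, Appendix A).

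Appendix A, footnote 6, sets the timing: "MRIs and labs (including AFP) will be performed 4 weeks (± 1 week) after each TACE cycle". In bilobar disease the cycle is complete only after both lobes are treated. Section 7.2 says "the second lobe must undergo chemoembolization within 4 weeks" (± 1 week) of the first lobe, and section 7.3 times the MRI from the second lobe.

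Section 11.5.1 fixes the survival clock: "Overall survival time will be calculated in months from the date of the first study TACE embolization to the date of death". It names the primary population: "The primary efficacy analysis of median overall survival will be performed on the ITT population". It then adds: "Survival analyses will also be performed for the Evaluable population". It gives no separate time origin, landmark or delayed entry for that added analysis.

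The rules for patients without a post-baseline MRI in section 11.5.2 (objective response) and section 11.5.6 (time to untreatable progression) concern the intent-to-treat (ITT) population. Neither covers Evaluable survival.

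**The concern.** A post-baseline scan is needed to score tumor response. It is not needed to know whether a patient is alive. Using it as an entry condition for survival selects patients on something that happens after the clock has started. The interval from first TACE to first MRI becomes immortal time: no Evaluable patient can die in it, yet all of them are credited with it.

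The result is upward bias in the Evaluable medians and in the one- and two-year survival rates, in both arms. There is also a blind spot. The device's rationale includes less systemic doxorubicin exposure and better tolerance in patients with poorer hepatic status (section 1). If early mortality differed between the arms in either direction, Evaluable survival could not show it.

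**Working it through.** **Inputs**

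- Median survival 16 months (cTACE) and 24 months (hqTACE), hazard ratio 1.500, two-sided 5%, 85% power, 196 per group for power, 255 per group enrolled (section 11.2).
- 218 deaths, or two years after the last patient's first TACE (section 11.5.1).
- MRI and second-lobe windows as in sections 7.2 and 7.3 and Appendix A.
- Assumptions made here: exponential survival; all 255 patients per arm are treated and none is excluded for another reason. The unilobar/bilobar mix is not stated, so a range is shown.

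**The plan's own figures**

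- Events (Schoenfeld): 4 × (1.960 + 1.036)² / (ln 1.5)² = 218.4, against 218 stated.
- Patients: Freedman events are 8.978 × (2.5/0.5)² = 224.5. Exponential death probabilities at 24 months are 0.646 and 0.500, mean 0.573. Then 224.5 / (2 × 0.573) = 195.8, so 196 per group. The flat 24-month follow-up is an assumption, but the match shows that the exponential model is consistent with the plan.
- Windows: reading each as plus or minus, the final response assessment in unilobar disease falls at 6 + 6 + 3 = 15 to 10 + 10 + 5 = 25 weeks. In bilobar disease it falls at 9 + 12 + 3 = 24 to 15 + 20 + 5 = 40 weeks. Both ranges match the Treatment and Assessment section. On the same reading the first MRI falls at 3 to 5 weeks (unilobar) and at 3 + 3 = 6 to 5 + 5 = 10 weeks (bilobar).

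**Deaths excluded and medians reported**

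For an MRI at L months, P(death before MRI) = 1 − 2^(−L/median). Among survivors to L, S(t) = 2^(−(t − L)/median), so the median counted from first TACE is the planning median plus L. One week is 0.23 month.

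| First MRI | L (months) | Die before MRI, cTACE / hqTACE | Expected deaths of 255 per arm | Total | Evaluable medians (months) |
|---|---|---|---|---|---|
| 3 weeks | 0.69 | 2.9% / 2.0% | 7.5 / 5.0 | 12.5 | 16.7 / 24.7 |
| 4 weeks | 0.92 | 3.9% / 2.6% | 10.0 / 6.7 | 16.6 | 16.9 / 24.9 |
| 8 weeks | 1.84 | 7.7% / 5.2% | 19.5 / 13.2 | 32.7 | 17.8 / 25.8 |
| 10 weeks | 2.30 | 9.5% / 6.4% | 24.2 / 16.4 | 40.6 | 18.3 / 26.3 |

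The first and last rows are the extremes: every patient unilobar and scanned at the earliest date, or every patient bilobar and scanned at the latest.

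One-year survival, 2^(−(12 − L)/median), rises in cTACE from 59.5% to 61.9% (4 weeks) or 64.4% (8 weeks), and in hqTACE from 70.7% to 72.6% or 74.6%. Two-year survival rises from 35.4% to 36.8% or 38.3%, and from 50.0% to 51.3% or 52.7%.

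**Treatment comparison**

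This was simulated with 255 per arm, censoring at 24 months and 3,000 runs. Hazard ratios are hqTACE over cTACE, so the planned 1.500 appears as 0.67. The excess is an assumed additional share of hqTACE patients dying before a 4-week MRI.

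| Assumed early excess on hqTACE | Equal hazards afterwards: ITT / Evaluable | Planned benefit afterwards: ITT / Evaluable |
|---|---|---|
| 0% | 1.00 / 1.00 | 0.67 / 0.67 |
| 3% | 1.05 / 1.00 | 0.71 / 0.67 |
| 5% | 1.08 / 1.00 | 0.74 / 0.67 |
| 10% | 1.16 / 1.00 | 0.82 / 0.67 |

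With no departure from proportional hazards the two populations agree. With an early excess, ITT registers it and Evaluable survival does not.

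**The case against.** The strongest reply is that nothing decisive rests on this analysis. The primary log-rank test, the site poolability analysis and the supportive Cox model are all specified on ITT. Evaluable survival is one sentence, with no alpha or decision rule attached. Early deaths also remain visible elsewhere: they count in ITT survival, and section 11.6.1 summarizes fatal and serious events by arm in the Safety population, which needs one TACE and no scan. All of this stands, and it limits the point to a minor one.

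Three stronger readings are tempting, and the documents do not support them.

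- A reader might infer that every death before week 5 (or week 10) is dropped. Exclusion depends on the patient's own scan: someone scanned at week 3 who dies at week 4 is in the population. The late-window counts are ceilings.
- A reader might infer that the treatment comparison is biased. Under the planning assumptions it is not. Bias needs early mortality that departs from the later hazard ratio. The documents give no early death rate, and the 3% to 10% above is assumed. Entry also requires a life expectancy of at least 6 months (section 3), so the hazard in the first weeks may be below the exponential one.
- A reader might infer that a planned check on the ITT result is defeated. The plan never gives Evaluable survival that role.

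What the reply does not remove is the upward shift in the medians and survival rates that the plan says it will report.

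**Conclusion.** The plan is wrong as written on a secondary-population analysis. The immortal time follows from the definitions alone, and no other section cures it. How many deaths it removes and how far it moves the medians and survival rates depend on exponential survival at the planning medians, on when scans are done and on the unstated share of bilobar patients. The shift in each median equals the time to the first MRI, which is roughly 1 to 2 months in the central cases.

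The trial's main conclusion is not at risk. The practical limit is on interpretation: agreement between Evaluable and ITT survival would say nothing about early harm or early benefit.

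**What to change.** In section 11.5.1, state that for overall survival the Evaluable population is all treated patients without major protocol violations, and keep the post-baseline MRI requirement for tumor response only. This costs one sentence and needs no new data. The exclusion for major protocol violations would remain, and the analysis should still be read with that in mind.

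If the MRI requirement is kept for survival, use delayed entry at each patient's first post-baseline MRI, or a landmark no earlier than week 10. Label the analysis accordingly, and report the excluded deaths by arm. A week-5 landmark is not enough: the first MRI in bilobar disease falls at about 6 to 10 weeks, so bilobar deaths between week 5 and the scan would still be excluded by definition.
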